13      Institutional research policies and procedures.

14        **1.1 Specific Aims and Hypothesis**

15        The primary aim of this study is to compare the 30 and 90-day overall/cumulative grade III or  
16        higher complication rates between patients with severe obstructive jaundice undergoing  
17        preoperative endoscopic biliary drainage with SEMS and patients undergoing direct surgical  
18        resection. In this study, **One arm undergoes preoperative biliary drainage followed by surgery and**  
19        **the other arm undergoes surgical resection** without prior biliary drainage. Secondary aims will be  
20        to compare surgical outcomes including mortality, intra-operative parameters, hospital length of  
21        stay, ICU length of stay, readmission rate and time to commencement of adjuvant treatment.

22        **1.2 Background and Rationale**

23        Despite the fact that endoscopic and percutaneous placement of biliary stents is technically  
24        successful in 90-95% of cases, routine preoperative biliary drainage for pancreatic cancer remains  
25        controversial.[4, 5] Pooled data from retrospective studies published over the past several years  
26        have shown similar rates of 30-day mortality after pancreaticoduodenectomy in those who have  
27        undergone biliary decompression as compared to those who have not. A few studies have  
28        suggested that routine preoperative drainage in patients undergoing surgery for cancer of the  
29        pancreatic head may increase overall complications, likely due to complication related to the  
30        endoscopy itself (i.e. pancreatitis, bleeding, perforation) and complications related to stent  
31        failure.[6] In the largest, multicenter, randomized trial to date, patients were randomly assigned  
32        to undergo either endoscopic preoperative biliary drainage for 4 to 6 weeks, followed by surgery,  
33        or surgery alone after diagnosis. In this study, endoscopic preoperative biliary drainage did not  
34        have a beneficial effect on the surgical outcome but rather was associated with an increase in  
35        serious complications.[7]

36  
37        On the other hand, outcome measures have not been standardized and the lack of complete data  
38        on surgical complications following preoperative drainage make direct comparisons difficult and  

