170 The stent will placed by ERCP and won't be removed before surgery unless indicated. Follow up  
171 phone calls to ascertain secondary endpoints will be made at 30 and 90 days.

172 5.7 Prior and Concomitant Therapy  
173 Subject in the study are to continue any medications that they are on. Those who are randomized  
174 to the intervention group may be asked to hold antiplatelet/anticoagulation agents prior to the  
175 ERCP in coordination with their prescribing doctor.

176 5.8 Blinding of Study Drug  
177 Unblinded study

178 **6.0 STUDY PROCEDURES**

179

180 **6.1 Study Visit Schedule**

181 **Screening:**  
182 Patients will be screened in clinic or if admitted as inpatients. Patient must satisfy the inclusion  
183 criteria listed above. Patient must carry a diagnosis of per-ampullary cancer. Basic labs will be  
184 withdrawn including CBC, CMP and INR.

185

186 **Randomization**  
187 **Peri-operative:** The patient will be admitted and labs will obtained including CBC, CMP and  
188 INR prior to surgery.

189

190 **Post-operative:**  
191 Visit 1: This will be scheduled 3-4 weeks after hospital discharge. Labs and imaging may be  
192 ordered by the surgeon if needed.

193 Follow-up  
194 Patients will be followed up to 90 days after the surgery. A phone call will be placed to the  
195 patient by research staff to ascertain secondary endpoints. Jefferson EMR will be accessed  
196 to ascertain primary endpoint data.

197

198 **7.0 STATISTICAL PLAN**

199 7.1 Sample Size Determination  
200 Based on previous data, we assumed an overall grade III or higher complication rate of  
201 50% in the control group. Although we are unsure of the expected rate in the pre-operative  
202 biliary stenting group, a 30% or greater reduction in the grade III or higher complication

would be meaningful. The sample size will be 100 subjects (50 per arm). We calculated power under various alternatives for the biliary stenting group complication rate using a two-group large-sample normal approximation test of proportions, with a one-sided significance level of 0.05, to test the null hypothesis that the grade III or higher complication rate in surgery with biliary stenting is greater than or equal to the control rate (50%). We have 84% power to detect a reduction if the true rate with biliary stenting is 25%, 66% power if the true rate is 30%, and 44% power if the true rate is 35%.

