## 7.2 Statistical Methods

Baseline characteristics will be summarized by randomization arm using means, standard deviations, and ranges for continuous variables and counts and frequencies for categorical variables.

Rates of grade III or higher complication rates will be estimated separately at 30 and 90 days. The risk difference will be calculated (stent minus control) with a one-sided 95% confidence interval. If the upper bound of the confidence interval is less than 0 at both times, surgery with biliary stenting will be considered effective at reducing the rate of grade III or higher complications.

Group comparisons with respect to continuous outcomes will be performed using two-sample t-tests or Wilcoxon rank sum tests. Comparisons for categorical outcomes will be performed using chi-square tests or Fisher's exact test. Comparisons for count outcomes will use Poisson regression. Kaplan-Meier analysis will be used to estimate the distribution of time-to-event outcomes. Groups will be compared using the log rank test.

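### The 84/66/44% power in Section 7.1 is for one comparison at an unnamed time point, but Section 7.2 requires success at both 30 and 90 days

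*Combined protocol and SAP*

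**What the plan says.** Section 7.1 rests on a single planning rate: "Based on previous data, we assumed an overall grade III or higher complication rate of" "50% in the control group". The rate is described as overall and carries no 30- or 90-day label. Power is then calculated for one large-sample test of two proportions, 50 patients per arm, "with a one-sided significance level of 0.05". The section reports: "We have 84% power to detect a reduction if the true rate with biliary stenting is 25" percent, then 66% at a stent-arm rate of 30% and 44% at 35%.

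Section 7.2 sets a different hurdle. "Rates of grade III or higher complication rates will be estimated separately at 30 and 90 days", each with a one-sided 95% confidence interval for the risk difference (stent minus control). Stenting is declared effective only "If the upper bound of the confidence interval is less than 0 at both times".

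Section 1.1 indicates that the rates accumulate: "The primary aim of this study is to compare the 30 and 90-day overall/cumulative grade III or" higher complication rates. A patient with an event by day 30 therefore also counts as having one by day 90. Sections 2.1 and 3.2 likewise name both times, so the double requirement is not a stray phrase in 7.2.

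**The concern.** The power in 7.1 belongs to a single test, and the decision in 7.2 depends on two. The two tests share patients and events but are not the same test: first events after day 30 change the counts, and one bound can be below 0 while the other is not. Anyone relying on 84/66/44% would be relying on the power of a rule the trial does not use.

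This matters because the stated power is already modest. Section 7.1 calls a reduction of 30% or more meaningful. If that is relative (50% to 35%; the text does not say), the stated power for it is only 44% before the second requirement is counted. A null result would be hard to interpret without the power of the actual rule.

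**Working it through.** **Inputs from the documents.** n = 50 per arm; control rate 0.50; stent rates 0.25, 0.30, 0.35; one-sided alpha 0.05, z = 1.645 (Section 7.1). Success requires rejection at both 30 and 90 days (Section 7.2). Rates are cumulative (Section 1.1).

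**Step 1: reproduce the plan's figures as one test.** With p̄ = (0.50 + p)/2:

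power = Φ{[(0.50 − p) − 1.645·√(2p̄(1−p̄)/50)] / √[(0.50·0.50 + p(1−p))/50]}

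For p = 0.25: p̄ = 0.375, null standard error 0.0968, alternative standard error 0.0935. So (0.25 − 1.645 × 0.0968)/0.0935 = 0.97 and Φ(0.97) = 83.4%. The other two rates give 65.7% and 44.9%. Exact binomial power of the same pooled test is 84.0/65.8/44.0%, which rounds to the stated 84/66/44%. The stated figures are therefore the power of one comparison.

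**Step 2: the bound.** P(success at 30 and at 90 days) ≤ min{P(success at 30), P(success at 90)}. Whichever time point the planning rates describe, single-test power there is 84/66/44%, and the both-times rule cannot exceed it. This step needs no outside figure.

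**Step 3: possible size of the loss.** The documents give no 30/90-day split, so every split below is an assumption. Exact enumeration, for each arm:

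- X30 ~ Bin(50, p30)
- late first events ~ Bin(50 − X30, (p90 − p30)/(1 − p30))
- X90 = X30 + late first events
- success = pooled z-test rejects at both times

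| Assumption | Power of both-times rule at stent rate 25/30/35% |
|---|---|
| Single test, as in 7.1 | 84.0/65.8/44.0 |
| (A) 50% is the 90-day rate; 95% of events in each arm by day 30 | 79.9/60.4/38.6 |
| (A) 90% by day 30 | 76.7/56.8/35.7 |
| (A) 80% by day 30 | 69.8/50.1/30.8 |
| (A) 70% by day 30 | 62.4/43.2/26.0 |
| (B) 50% is the 30-day rate; both arms rise in proportion, 60–95% of events by day 30 | 82.3–84.0/62.4–65.6/39.4–42.7 |
| (C) 50% is the 30-day rate; 5% of event-free patients in each arm have a late first event | 76.8/57.2/36.6 |
| (C) 10% | 71.0/51.6/32.4 |
| (C) 20% | 60.5/42.9/26.5 |
| (D) 50% is the 30-day rate; late first events in controls only | 84.0/65.8/44.0 |

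Two examples show the mechanism.

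- In (A) at 90%, the 30-day rates are 0.9 × 50% = 45% and 0.9 × 25% = 22.5%. Single-test power at day 30 is 78.8%, and requiring day 90 as well brings it to 76.7%.
- In (C) at 10%, the 90-day rates are 0.50 + 0.10 × 0.50 = 0.55 and 0.25 + 0.10 × 0.75 = 0.325. The difference shrinks from 25 to 22.5 points, and power at day 90 alone is 72.9%.

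**Step 4: type I error.** With no effect and a 50% 90-day rate in both arms, the both-times rule rejects in 2.1–3.4% of trials (70–95% of events by day 30), against 4.5% for a single test at that rate. The rule is conservative.

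**Step 5: interval type.** Section 7.2 does not say which confidence bound will be used. With the unpooled Wald bound the single-test baseline is 84.7/67.1/45.2% and (A) at 90% is 77.3/57.9/36.8%, about 1 point higher throughout.

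**The case against.** The arithmetic in 7.1 is correct for the test it describes, and 7.1 nowhere claims to give the power of the two-time rule. That is true. The defect is that the figures do not match the decision rule, not that they were miscalculated.

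The loss may also be zero. It is zero if all events occur by day 30, or if late first events fall only on controls, and it is small if both arms rise in proportion after day 30. This stands as well, but the plan gives the reader no means of telling which case applies.

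The sizes depend on the splits chosen. This is fair: extending (A) to 60% of events by day 30 gives 54.9/37.0/21.8%, a loss of up to 84.0 − 54.9 = 29.1 points, so no upper end of the range should be read as a finding. Some cells are also extreme: (B) at 60% implies a 90-day control rate of 0.50/0.60 = 83%.

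The word ceiling needs two qualifications. The planning rates must apply at day 30 or day 90. And with the unpooled Wald bound the ceiling is about 85/67/45%, roughly 1 point above the stated figures.

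It can be argued that an overall rate naturally means cumulative to the end of follow-up at 90 days. That reading is reasonable but not certain. It would make (A) the relevant case, where power is lost at every assumed split.

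Finally, requiring both times is a legitimate conservative choice. It can stay, but it needs its own power.

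**Conclusion.** The concern holds. The 84/66/44% is single-comparison power and is a ceiling, to within about 1 point for the choice of interval, on the power of the rule in 7.2. This rests only on the two sections and on the planning rates applying at one of the two times.

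The size of the shortfall is not determined by the documents. Under the tabulated assumptions it runs from none to about 23 points (84.0 − 60.5 = 23.5 in (C) at 20%), and it would be larger with later events. With the 50% read as a 90-day rate and 80–95% of events by day 30, power is about 70–80/50–60/31–39%.

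This is a misstatement of power only. The test remains valid and type I error is not inflated. It should be fixed, because the figure is one that readers will use to judge the trial.

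**What to change.** In Section 7.1, state which time point the 50% control rate refers to, give the assumed 30- and 90-day grade III or higher rates in each arm, and replace 84/66/44% with the power of the both-times rule under those rates. If the split is uncertain, a short table over a plausible range will do. The calculation should use the confidence bound intended for 7.2.

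The cost is a few sentences. The analysis and the sample size need not change, although the stated power will probably look less favourable.

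An optional alternative, to be settled before any outcome data are seen, is to make one time point the sole decision endpoint and the other secondary. It departs from Sections 1.1, 2.1, 3.2 and 7.2, which treat both as primary. It also restores 84/66/44% only if 50% is the control rate at the time chosen. For example, if 50% is the 30-day rate and 10% of event-free patients in each arm have a late first event, the power of a 90-day-only rule is about 73/55/37%.

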65 obstruction prior to surgery. This represents the first biliary metal stent with labeling to support  
66 pre-operative drainage in the US.

67 **1.4 Preclinical Data**

68 Please see clinical data below

69 **1.5 Clinical Data to Date**

70 A recent meta-analysis of 1989 patients showed that SEMS have higher stent insertion success,  
71 lower risk of stent occlusion, lower re-intervention rate, fewer therapeutic failures, and fewer  
72 episodes of cholangitis compared to plastic stents making them the optimal choice for biliary  
73 decompression.[8] Also a recent randomized controlled trial confirmed that SEMS are superior to  
74 plastic stents with regard to functional stent time and showed that the total health care cost is  
75 similar for placing SEMS or plastic stents even in patients with survival less than 3 months

76 **1.6 Dose Rationale and Risk/Benefits**

77 The study doesn't involve drug administration.

78 **2.0 STUDY OBJECTIVES**

79 **2.1 Primary Objective:**

80 The primary aim of this study is to compare the 30 and 90-day overall complication rates between  
81 patients with severe obstructive jaundice undergoing preoperative endoscopic biliary drainage  
82 with SEMS and patients undergoing direct surgical resection.

83 **2.2 Secondary Objective:**

84 Secondary aims will be to compare surgical outcomes including hospital length of stay, ICU  
85 length of stay, readmission rate, disposition from hospital, emergency room visits, urgent care  
86 center visits and time to commencement of adjuvant treatment.

87 **3.0 STUDY DESIGN**

88 **3.1 General Design**

89 This is a Randomized controlled trial.

92 ERCP will be performed on those who are randomized to the intervention group with 24 hours of  
93 randomization. The patient will be followed at 30 days and 90 days post-operatively.

94 **3.2 Primary Study Endpoints**

95 30 and 90 day- complication rates between patients with severe obstructive jaundice undergoing  
96 preoperative endoscopic biliary drainage with SEMS and patients undergoing direct surgical  
97 resection

98 **3.3 Secondary Study Endpoints**

99 Secondary aims include the total number of complications, intraoperative estimated blood loss,  
100 number of required fluid boluses, postoperative hospital LOS, readmission rate, disposition from  
101 hospital, time to commencement of adjuvant treatment, emergency room visits, urgent care center  

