102 visits, and perioperative mortality. Complications will include pancreatic fistula, delayed gastric  
103 emptying, intra-abdominal abscess, cardiac complications, respiratory complications, deep vein  
104 thrombosis, pulmonary embolism, urinary tract infection, wound infection, acute renal failure,  
105 hemorrhage, hepaticojjunostomy leak, and duodenojjunostomy leak. Pancreatic fistula was  
106 defined and graded according to the International Study Group of Pancreatic Fistula criteria.  
107 Delayed gastric emptying was defined and graded according to the International Study Group of  
108 Pancreatic Surgery. Wound infections and urinary tract infection were defined according to the  
109 Centers for Disease Control and Prevention guidelines. Cardiac complications were defined  
110 according to the American College of Cardiology and renal complications were defined by the  
111 Acute Dialysis Quality Initiative.

112 **3.4 Primary Safety Endpoints**

113 Both SEMS placement and direct surgical resection are considered acceptable standard of care  
114 practices.

115 **4.0 SUBJECT SELECTION AND WITHDRAWAL**

116 **4.1 Inclusion Criteria**

117 -Adult patients age >18 regardless of gender or ethnicity  
118 -Patients with peri-ampullary pancreatic cancer.  
119 -Patients with serum bilirubin greater than 10mg/dL  
120 -Adequate birth control

121 **4.2 Exclusion Criteria**

122 -Patients with evidence of distant metastasis on CT or MRI  
123 -Patients anticipated to require vascular reconstruction  
124 -Patients with cholangitis  
125 -Patients who previously underwent biliary decompression for cholangitis by ERCP or PTC  
126 -Patients with low performance score (Karnofsky performance status scale < 50)  
127 -Patients with known preexisting liver disease with associated elevated bilirubin  
128 -Patients who are pregnant or actively breast feeding.

129 **4.3 Gender/Minority/Pediatric Inclusion for Research**

130 Any patient can be included if older than 18 years of age irrespective of gender, color, or  
131 ethnicity.

133 4.4 Subject Recruitment and Screening

134 One Hundred patients older than 18 years with periampullary cancer presenting with jaundice and  
135 total bilirubin greater than 10mg/dL will be included in the study.

136 Patients will be recruited from clinic (gastroenterology and pancreaticobiliary surgery) or when  
137 admitted to the hospital for workup and/or management and will be consented at that time.

138

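### Section 7.2 analyses counts by Poisson regression with no provision for variance other than the mean, so the standard errors for total complications may be too small or slightly too large (minor; secondary outcomes only)

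*Combined protocol and SAP*

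**What the plan says.** Section 7.2 (Statistical Methods) covers count outcomes in one sentence: "Comparisons for count outcomes will use Poisson regression". No variance estimator, dispersion check or alternative model is named there or elsewhere. In the same paragraph, continuous outcomes have two possible methods (t-test or Wilcoxon) and so do categorical outcomes (chi-square or Fisher's exact).

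The outcomes concerned are in section 3.3 (Secondary Study Endpoints). Two are clearly counts:
- the total number of complications: "Secondary aims include the total number of complications, intraoperative estimated blood loss";
- fluid boluses: "number of required fluid boluses, postoperative hospital LOS, readmission rate, disposition from".

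Emergency room and urgent care visits are also listed, but the document does not say whether they are analysed as counts or as yes/no. Section 3.3 names 13 complication types, ending with "hemorrhage, hepaticojjunostomy leak, and duodenojjunostomy leak".

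The plan's tests with a stated level are those of the primary outcome, "with a one-sided significance level of 0.05" in section 7.1 and a one-sided 95% interval in 7.2. Secondary outcomes have no stated level, sidedness or success rule.

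**The concern.** With its usual model-based variance, Poisson regression takes each patient's count to have variance equal to its mean. A total over many complication types need not behave like that. If some patients are at higher risk of many types at once, the totals vary more than the model allows. Rate-ratio intervals are then too narrow and p-values too small.

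Mixed risk is plausible from the eligibility criteria. Section 4.1 admits any adult over 18 and "Patients with serum bilirubin greater than 10mg/dL", with no upper limit. Section 4.2 excludes only "Patients with low performance score (Karnofsky performance status scale < 50"), so performance status may range widely.

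Total complications is the secondary outcome closest to the primary question. An interval that is too narrow could be read as support for or against stenting. Section 5.8 says the study is unblinded, so a variance estimator left open until analysis could be chosen with the results in view.

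**Working it through.** **1. The plan's own figures.** Section 7.1 states power for the primary binary outcome only: 84%, 66% and 44% at stent-arm rates of 25%, 30% and 35%, with 50% in controls, 50 per arm and one-sided 0.05. The formula is power = Φ((d − 1.645·se0)/se1), with pooled se0 and unpooled se1. At 25%:
- se0 = √(2·0.375·0.625/50) = 0.0968
- se1 = √((0.25 + 0.1875)/50) = 0.0935
- power = Φ((0.25 − 0.1593)/0.0935) = 83.4%

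The other two come to 65.7% and 44.9%. All agree within one point. None uses the Poisson model, so none is touched by this point.

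**2. Effect of a given variance/mean ratio.** Call the ratio φ and take it as equal in both arms. The model standard error is then 1/√φ of the true one. Two-sided error is 2·(1 − Φ(1.96/√φ)); one-sided error is 1 − Φ(1.645/√φ). The document gives no φ and no level, so both are assumed.

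| φ | SE, model/true | two-sided 5% | one-sided 5% | coverage of 95% interval |
|---|---|---|---|---|
| 1.5 | 0.82 | 11.0% | 9.0% | 89% |
| 2 | 0.71 | 16.6% | 12.2% | 83% |
| 3 | 0.58 | 25.8% | 17.1% | 74% |

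Simulation with negative-binomial counts, 50 per arm, 40,000 trials per setting and means of 1.5 to 3 gave two-sided errors of 10.5–10.9%, 16.5–16.7% and 25.3–25.8%.

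**3. What φ might be for total complications.** This step assumes that each of the 13 types counts at most once and has the same probability p. Section 3.3 does not say so. With average pairwise correlation ρ, the variance of the total is 13p(1−p)(1+12ρ), so φ = (1−p)(1+12ρ).

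- *Independent types (ρ = 0).* φ = 0.90 at p = 0.10 and 0.85 at p = 0.15. Simulated error is 3.8% and 3.1%, slightly conservative.
- *Break-even.* φ exceeds 1 when ρ > p/(12(1−p)). That is 0.1/10.8 = 0.009 at p = 0.10 and 0.15/10.2 = 0.015 at p = 0.15. Only the average over the 78 pairs matters.
- *Only five clinically linked types correlated* (fistula, abscess, hemorrhage and the two leaks: 10 of 78 pairs). φ = (1−p)(1+20ρ/13), where ρ is now the correlation within those pairs. Break-even is ρ = 0.072 at p = 0.10 and 0.115 at p = 0.15. These are the same averages as above (0.072·10/78 = 0.009). At ρ = 0.20, φ is 1.18 or 1.11 and simulated error 6.9% or 6.1%.

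**4. Patients at different risk.** Suppose 25% of patients have a higher probability of every type and the other 75% have 0.10. The variance is 13·E[p(1−p)] + 169·Var(p).

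| high-risk p | mean | variance | φ | simulated two-sided error |
|---|---|---|---|---|
| 0.20 | 1.625 | 1.3975 + 0.3169 = 1.714 | 1.05 | 5.4% |
| 0.30 | 1.95 | 1.56 + 1.2675 = 2.828 | 1.45 | 10.2% |
| 0.40 | 2.275 | 1.6575 + 2.8519 = 4.509 | 1.98 | 16.2% |

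A different model, with a shared logit-normal patient risk and average p of 0.05 to 0.15, gave error of 6.1–6.9% at a between-patient SD of 0.5 and 11.8–16.9% at an SD of 1.0.

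**5. Alternatives.** Over all the 40,000-trial null settings, Pearson scaling with t on 98 degrees of freedom had two-sided error of 4.7–5.3%, and robust errors 5.2–6.1%. At lower means robust errors do less well: 7.4% at a mean of 0.5 and φ = 3.

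**The case against.** The strongest reply is that this is a matter of detail. Section 7.2 names a model family, and scaled or robust errors are compatible with it. The rest of the paragraph is equally brief: it does not say when Wilcoxon or Fisher's test applies. No decision rule depends on the secondary outcomes. That stands, and it is why the point is minor. It does not dispose of the point, because the default reading of the sentence is the unscaled analysis, and a concrete alternative holds its error rate whether φ is above or below 1.

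The second reply is that heterogeneity is not shown. Section 4.2 also narrows the population: it excludes distant metastasis, anticipated vascular reconstruction, cholangitis, prior decompression for cholangitis, and known liver disease with raised bilirubin. The Study Summary names one centre. This too stands. Overdispersion is plausible but undocumented, and moderate heterogeneity adds little error.

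A reader might infer that clinically linked complications alone make the test seriously liberal. The document gives no correlations, and step 3 shows that five linked types add only one or two points of error even at a correlation of 0.20. A reader might also take 26% as the expected error. It requires φ = 3 and a two-sided 5% test, and the document supports neither.

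**Conclusion.** The gap is real and minor. Section 7.2 makes no allowance for variance different from the mean. For total complications, the resulting error could be slightly conservative (3 to 4% two-sided with independent types), about nominal (about 5.5% when a quarter of patients have double risk), or clearly liberal (11%, 17% or 26% two-sided, 9%, 12% or 17% one-sided, at φ of 1.5, 2 or 3). Nothing in the document places this trial within that range. The correlation thresholds of 0.009 and 0.015 also assume 13 equally likely yes/no types.

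The direction is argued only for total complications. For fluid boluses it is unknown, and visits are affected only if analysed as counts. It would be wrong to infer that the trial's main conclusion is at risk: the primary analysis is a risk difference, and neither it, the sample size nor the stated power uses the Poisson model.

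**What to change.** In section 7.2, replace the sentence on count outcomes with: *Count outcomes will be compared by Poisson regression with Pearson-scaled (quasi-Poisson) standard errors and a t reference distribution on the residual degrees of freedom; the rate ratio and its confidence interval will be reported.* It would help to name the outcomes (total complications, fluid boluses, and the visit outcomes if they are to be counts). Robust (sandwich) errors are an acceptable alternative.

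The cost is one sentence and one software option. With no overdispersion, intervals widen by about 1% (1.9845/1.96). At an assumed rate ratio of 0.7 and control mean of 2, two-sided power falls from 63% to 62%.

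With φ of 1.5, 2 or 3, intervals widen by √φ·1.9845/1.96 = 1.24, 1.43 or 1.75, and power in the same setting is about 46%, 36% or 26%. The unscaled test would show about 60% throughout, but only with the inflated error in step 2. The wider intervals have the right coverage (94.9–95.1% in simulation).
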